#### **8.2.3.1. Adverse drug reactions**

- **All adverse drug reactions**

The number and proportion of patients with adverse drug reactions will be tabulated by SOC and PT.

- **Details of adverse drug reactions**

ADRs categorized by each of the following factors will be summarized in terms of number and proportion of patients with ADRs by SOC and PT:

- Seriousness [serious, non-serious]
- Known/Unknown [known, unknown]
- Action taken (additional treatment for the AE) [performed, not performed]
- Action taken [discontinuation of treatment, temporary suspension or dose reduction, none]
- Outcome [fatal, not recovered, recovered with sequelae, recovering, resolved/recovered, unknown]
- CTCAE Grade (1) [1, 2, 3, 4, 5, unknown]
- CTCAE Grade (2) [ $< 3$ ,  $\geq 3$ , unknown]

Multiple occurrences of the same adverse drug reaction (with the same PT) in the same patient will be handled as follows in the summary:

- Seriousness: If both serious and non-serious events of the same AR occurred in the same patient, the patient will be counted as one with a serious reaction.
- Known/Unknown: If both known and unknown events of the same AR occurred, the patient will be counted as one with an unexpected reaction.
- Action taken: If multiple types of actions were taken for the same AR in the same patient, one action will be adopted in the order of priority of "discontinuation of treatment", "temporary suspension or dose reduction", and "none".
- Outcome: See below
- CTCAE Grade: If there are multiple grades, the highest grade will be used.

In the summary by outcome, multiple events of the same AR in the same patient will be handled as follows:

- Outcome: If multiple different outcomes were reported, one category of outcome will be adopted from "fatal", "not recovered", "unknown", "recovered with sequelae", "recovering", and "resolved/recovered" with priority in this order.

Each SOC and PT of serious ADRs will be summarized by outcome.

- **Safety specification**

Patients who experienced the events identified as the safety specification will be summarized in terms of n and proportion. Similar summary will also be performed by CTCAE Grade [ $< 3$ ,  $\geq 3$ , unknown].

In addition, events identified as the safety specification will be summarized in terms of number and proportion of patients with such events for each SOC and PT by actions taken and outcome thereof.

- **Timing of onset of adverse drug reactions**

For ADRs that occurred in at least 10% of patients, number and proportion of patients with the ADRs will be summarized for each SOC and PT by category of timing of initial onset [ $< 4$  weeks after the start of treatment,  $\geq 4$  weeks to  $< 8$  weeks,  $\geq 8$  weeks to  $< 12$  weeks,  $\geq 12$  weeks to  $< 16$  weeks,  $\geq 16$  weeks to  $< 20$  weeks,  $\geq 20$  weeks to  $< 24$  weeks,  $\geq 24$  weeks].

In addition, time to event will be summarized as per Section 8.1.4 with event being the first onset of the AR. The analysis will be performed with the following specifications:

- Analysis set: SAS
- Handling of patients with no AR: Censored at 28 days after the final dose of this drug.
- Time points for rate estimation: Weeks 1, 2, 3, 4, 8, 12, 16, 20, and 24
- **Occurrence of adverse drug reactions by inclusion/exclusion in the safety analysis set**

For the population of patients whose case report form was collected, a listing of ADRs in patients excluded from the SAS will be prepared. In addition, excluded patients with ADRs will be summarized by SOC and PT.

- **VOD/SOS**

Events of VOD/SOS reported as AR will be analyzed. Events included in each analysis will not be limited to events of initial onset. Unless otherwise specified, VOD/SOS events will be summarized respectively for each of the following categories.

- VOD/SOS that occurred after the start of this drug (Use the SAS as the analysis set.)
- VOD/SOS that occurred with absence of HSCT after the start of this drug (Same as above): Here, "absence of HSCT" means that VOD/SOS occurred with no HSCT or occurred before any HSCT.
- VOD/SOS that occurred with presence of HSCT after the start of this drug (Patients in the SAS who underwent HSCT after the start of this drug will be analyzed)

**Occurrence of VOD/SOS:** The number of patients with VOD/SOS and its proportion will be summarized. Among the factors listed in "Details of adverse drug reactions" in Section 8.2.3.1, n and proportion will be summarized with respect to each of the following factors: Action taken [discontinuation, temporary suspension or dose reduction, none], Outcome [fatal, not recovered, recovered with sequelae, recovering, resolved/recovered, unknown], CTCAE Grade (1) [1, 2, 3, 4, 5, unknown], and CTCAE Grade (2) [ $< 3$ ,  $\geq 3$ , unknown].

**Timing of onset of VOD/SOS:** To analyze the timing of onset of VOD/SOS, summary statistics will be performed as per Section 8.1.1, for the following kinds of time.

- Time from the final dose of this drug: Time (weeks) from the final dose of this drug to the onset of VOD/SOS
- Time from HSCT: Time (weeks) from the first HSCT after the start of this drug to the onset of VOD/SOS. Only VOD/SOS events that occurred with presence of HSCT after the start of this drug will be included in this analysis (Similar limitation shall also apply to the analysis set).

Patients with VOD/SOS will be counted by each of the following timing factors. For each timing factor, data will also be summarized in a histogram (The longitudinal axis is frequency. The width of each onset period will depend on the actual duration of the period).

- Time from the final dose of this drug: < 2 weeks, ≥ 2 weeks to < 4 weeks, ≥ 4 weeks to < 8 weeks, ≥ 8 weeks to < 12 weeks, ≥ 12 weeks to < 16 weeks, ≥ 16 weeks
- Time from HSCT 1: < 2 weeks, ≥ 2 weeks to < 4 weeks, ≥ 4 weeks to < 6 weeks, ≥ 6 weeks to < 8 weeks, ≥ 8 weeks. This time is defined as the time starting from the first HSCT after the start of this drug.
- Time from HSCT 2: ≤ 3 weeks, > 3 weeks. This time is defined as the time starting from the first HSCT after the start of this drug.

Regarding the timing of onset of events described in "Timing of onset of adverse drug reactions" in Section 8.2.3.1, data will be analyzed with the following specifications.

- Analysis set: Patients who finished the survey (Patients who are recorded as discontinued in the "Record of continued/discontinued survey [treatment period]" in the case report form or patients for whom "Record of continued/discontinued survey [follow-up period]" in case report form is filled in. The latter means the survey is discontinued and completed for the patient.)
- Handling of patients who did not experience ADRs: If the survey had been discontinued for the patient, data shall be censored on the date of discontinuation based on the "Record of continued/discontinued survey" in the case report form; if the survey had been completed for the patient, data shall be censored on the last observation date defined in Section 7.
- Time points for rate estimation: Every 4 weeks from Week 4 to Week 52

For individual patients who experienced VOD/SOS, graphs will be prepared to indicate the start of this drug, the date(s) of HSCT after the start of this drug (only for those who underwent HSCT), the onset of VOD/SOS, the death (only for those who died), and timing of completion of the observation period or discontinuation of the survey, using the date of the last dose of this drug as the origin and using month as the time unit. The graphs will be displayed in ascending order of the time from the last dose of this drug to the onset of VOD/SOS.

**Performance of HSCT:** Performance of HSCT and occurrence of VOD/SOS will be summarized in terms of n and proportion with respect to the following specifications. The denominator of a proportion is the number of patients included in the 1-step higher itemization level.

- Safety Analysis Set
  - HSCT not performed (not performed before and after the start of this drug)
  - HSCT performed
    - ◊ HSCT performed before the start of this drug
      - HSCT not performed after the start of this drug
    - ◊ HSCT performed after the start of this drug
      - HSCT not performed before the start of this drug
      - HSCT performed before the start of this drug (performed both before and after the start of this drug)
  - VOD/SOS occurred
    - ◊ HSCT not performed before the start of this drug
    - ◊ HSCT performed before the start of this drug

- ◊ Occurred with no HSCT performed after the start of this drug or occurred before HSCT
  - HSCT not performed before the start of this drug
  - HSCT performed before the start of this drug
- ◊ Occurred after HSCT performed after the start of this drug
  - HSCT not performed before the start of this drug
  - HSCT performed before the start of this drug (performed both before and after the start of this drug)

**Exploration of factors associated with the occurrence of VOD/SOS (subgroup analyses):** Patients who experienced VOD/SOS after the start of this drug and patients who experienced VOD/SOS with HSCT performed after the start of this drug will be summarized in terms of n and proportion by each of the following factors selected from those specified in Section 5.4. In addition, risk ratios for the proportion of patients with the AR for different subgroups will be determined as per Section 8.1.3 and presented graphically. If, however, there is a category with less than 10 patients and after reconsideration it is considered difficult to determine the risk ratio for the category, it will not be determined for the relevant category. To investigate correlation between factors and occurrence of the ADR, statistical tests specified in Section 8.1.3 will be performed.

- Age [ $< 15$  years,  $\geq 15$  to  $< 65$  years,  $\geq 65$  years]
- Age [ $< 18$  years,  $\geq 18$  to  $< 55$  years,  $\geq 55$  years]
- Age [ $< 15$  years,  $\geq 15$  to  $< 40$  years,  $\geq 40$  years]
- Hepatic impairment
- Medical history (past) - VOD/SOS
- Medical history (past) - Hepatitis or hepatic disease
- Medical history (present) - VOD/SOS
- Medical history (present) - Hepatitis or hepatic disease
- ECOG PS before the start of this drug [ $0, 1, \geq 2$ , not performed]
- AST and ALT levels immediately before the start of this drug
- $\gamma$ -GTP level immediately before the start of this drug
- Total bilirubin level immediately before the start of this drug
- Platelet count immediately before the start of this drug
- Peripheral blast count immediately before the start of this drug
- Salvage line of the induction treatment with this drug
- HSCT before the start of this drug
- HSCT after the start of this drug

Similarly, VOD/SOS that occurred with HSCT performed after the start of this drug will be analyzed with respect to the following factors:

- Type of the first HSCT after the start of this drug
- Donor of the first HSCT after the start of this drug
- Conditioning with alkylating agent for the first HSCT after the start of this drug
- Conditioning with busulfan for the first HSCT after the start of this drug

- ECOG PS before conditioning for the first HSCT after the start of this drug [0, 1, ≥ 2, not performed]
- AST and ALT levels before conditioning for the first HSCT after the start of this drug
- γ-GTP level before conditioning for the first HSCT after the start of this drug
- Total bilirubin level before conditioning for the first HSCT after the start of this drug
- Platelet count before conditioning for the first HSCT after the start of this drug
- Peripheral blast count before conditioning for the first HSCT after the start of this drug
- Time from the date of final dose of this drug to the date of the first HSCT after the start of this drug
- Treatment cycles [1 cycle, 2 cycles, 3 cycles, 4 cycles, 5 cycles, 6 cycles, > 6 cycles]
- Treatment cycles [< 3 cycles, ≥ 4 cycles]

Listings that account for the occurrence of VOD/SOS and other features in patients who experienced VOD/SOS will be prepared.

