8.8.9. Records of investigation discontinuation

For patients who withdraw from the investigation during the observation period, enter the date of discontinuation. For the main reason for discontinuation, i.e., why the investigation cannot be continued, select one of the following options.

(Not making another visit, death, transfer to another hospital or department, or other)

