#### 8.1.4. Time-to-event data

For time-to-event data, the median, 1st quartile, and 3rd quartile will be determined using the Kaplan-Meier method. The rate at each time point will also be determined. To estimate CIs, log-log transformation will be used (this corresponds to specifying loglog under the conftype option in the proc lifetest statement of the SAS® lifetest procedure). In addition, Kaplan-Meier plots will be presented.

When time data are compared between subgroups using the Kaplan-Meier method, the hazard ratio of event occurrence and its 95% CI will be determined using the Cox proportional hazards model (ties handled by the Breslow method). In addition, the hazard ratio and its 95% CI will be presented graphically.

In the analysis of time data with competing risks, the cumulative incidence rate at each time point that takes into account competing risks will be determined (this corresponds to using the event code option in the time statement of the SAS® lifetime procedure). The standard error is to be estimated by the delta method. In addition, the time course of cumulative incidence will be graphically presented.

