#### **Continuation/discontinuation of survey (treatment period and follow-up period)**

Definition of the timing 1: < 4 weeks after the start of this drug,  $\geq$  4 weeks to < 8 weeks,  $\geq$  8 weeks to < 12 weeks,  $\geq$  12 weeks to < 16 weeks,  $\geq$  16 weeks to < 20 weeks,  $\geq$  20 weeks to < 24 weeks,  $\geq$  24 weeks to < 52 weeks,  $\geq$  52 weeks, entire period

Definition of the timing 2: < 4 weeks after the end of this drug,  $\geq$  4 weeks to < 12 weeks,  $\geq$  12 weeks to < 24 weeks,  $\geq$  24 weeks to < 48 weeks,  $\geq$  48 weeks, entire period

- Transfer to another hospital**

A patient is defined to have been transferred, if the patient's information at the transferred hospital is linked to the patient's information at the original hospital through the case report form prepared at the transferred hospital. For the SAS and EAS, patients will be summarized by each of the following factors, as per Section 8.1:

- Transfer to another hospital [absent, present]
- Timing of transfer (treatment period, follow-up period) \* The timing will be determined referring to the record of survey continuation/discontinuation in the original hospital's case report form. The denominator will be the number of patients with transfer.

- Summary of excluded patients**

Patients excluded from the SAS, those excluded from the EAS, and reasons for exclusion will be listed.

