### **8.2.3. Safety analyses**

Adverse drug reactions (ADRs) and adverse events (AEs) that occurred in the following periods will be collected for summary: for ADRs and AEs other than VOD/SOS, those that occurred from the start of this drug to 28 days after the final dose of this drug will be collected; for ADRs and AEs of VOD/SOS in patients who did not undergo HSCT within 52 weeks after the start of this drug, those that occurred within 52 weeks after the start of this drug will be collected; for ADRs and AEs of VOD/SOS in patients who underwent HSCT within 52 weeks after the start of this drug, those that occurred within 52 weeks after the last HSCT will be collected. The listings will include all events reported in this survey.

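### Onset analysis for adverse drug reactions (SAP 8.2.3.1): patients without the reaction are censored 28 days after the last dose even when death or loss to follow-up ended observation sooner

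*SAP*

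**What the plan says.** SAP 8.2.3.1, under the timing of onset of ADRs, specifies a time-to-first-onset analysis for ADRs seen in at least 10% of patients. The population is the whole safety set ("Analysis set: SAS"). The censoring rule is "Handling of patients with no AR: Censored at 28 days after the final dose of this drug". The output is "Time points for rate estimation: Weeks 1, 2, 3, 4, 8, 12, 16, 20, and 24". SAP 8.1.4 supplies the estimator: "the median, 1st quartile, and 3rd quartile will be determined using the Kaplan-Meier method". That section also describes a competing-risk cumulative incidence, but the ADR onset analysis names no competing event.

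The 28-day limit matches the collection window in SAP 8.2.3: for ADRs other than VOD/SOS, "those that occurred from the start of this drug to 28 days after the final dose of this drug will be collected".

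Both documents expect patients to leave before that limit. Protocol 8.8.9 records a discontinuation date and a main reason, with the options "Not making another visit, death, transfer to another hospital or department, or other". SAP 8.2.1 tabulates survey discontinuation with a first category for exactly this interval: "Definition of the timing 2: < 4 weeks after the end of this drug".

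For VOD/SOS onset, the same SAP section has a different rule. If the survey was discontinued, "data shall be censored on the date of discontinuation"; if it was completed, censoring is at the last observation date.

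**The concern.** Final dose plus 28 days is the right end of follow-up for a patient who was observed that long. It is not right for one who died on day 5 after the last dose, or who stopped attending then. Under the rule as written, that patient stays in the risk set until day 28, although no ADR can be recorded in the interval. Each later event is then divided by too many patients.

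Nothing elsewhere repairs this. Exclusions f and g in SAP 5.1 remove only patients with no adverse event information at all, not those observed part of the way. SAP 7 imputes missing death and survival dates but does not change this censoring date. SAP 8.1.4 is silent on it.

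At stake are the planned onset rates up to Week 24. They form part of the safety description in a population with relapsed or refractory leukaemia, where exit soon after the last dose is plausible.

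**Working it through.** **Plan's own figure.** None is stated for this analysis. The only power figure (80.4% with 176 patients) belongs to the VOD/SOS risk-factor comparison. It recomputes to 80.4% with 18.45% against 6.15%, and this point does not affect it.

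**Mechanism by hand (hypothetical).** Take ten patients. One has the ADR on Day 10. Four without it had their last dose on Day 15 and leave on Day 20, so the rule keeps them to Day 15 + 28 = Day 43. The other five continue treatment. One of them has the ADR on Day 30 and another on Day 50.

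| Handling of the four leavers | Through Day 30 | Through Day 50 |
|---|---|---|
| As written (kept to Day 43) | 1 − (9/10)(8/9) = 20% | 1 − (9/10)(8/9)(3/4) = 40% |
| Censored at exit | 1 − (9/10)(4/5) = 28% | 1 − (9/10)(4/5)(3/4) = 46% |
| Exits are deaths, competing event | 1/10 + (1/2)(1/5) = 20% | 20% + (1/2)(4/5)(1/4) = 30% |

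In the last row, 1/2 = (9/10)(5/9) is the share alive and ADR-free after Day 20. While the dead remain in the risk set, the planned estimate equals the competing-risk value. Once they are dropped at Day 43 as if censored, it rises above that value. It stays below the censor-at-exit value throughout.

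**Size for live losses (simulation, all inputs assumed).** Each scenario has 200,000 patients: 1 to 4 cycles with probabilities 40/30/20/10%, a constant ADR hazard, and a given share leaving uniformly within 28 days of the last dose, unrelated to ADR risk. Cells show the estimate as written / censored at exit, in %.

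| Leaving early | True 8-week ADR risk | Week 4 | Week 8 | Week 12 | Week 16 |
|---|---|---|---|---|---|
| 10% | 20% | 10.5 / 10.6 | 19.7 / 20.0 | 27.9 / 28.4 | 35.4 / 36.2 |
| 10% | 50% | 29.2 / 29.4 | 49.6 / 50.2 | 64.1 / 64.9 | 74.2 / 75.2 |
| 20% | 20% | 10.4 / 10.6 | 19.5 / 20.1 | 27.6 / 28.6 | 34.4 / 35.9 |
| 20% | 50% | 28.7 / 29.2 | 48.7 / 49.9 | 62.9 / 64.6 | 73.0 / 75.1 |

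Censoring at exit recovers the true values to within about 0.3 points.

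Other runs took 15 to 25% leaving. With hazards of 0.006 and 0.012 per day, the Week 12 shortfall was about 0.7 to 1.6 points. For a rarer ADR it was 0.4 to 0.6 points. At Week 4 it was 0.2 points or less. The table's treatment durations are short, which is why it reaches 1.7 points at Week 12 and 0.5 at Week 4 with 20% leaving.

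**Size for deaths.** Here 25% exit within 28 days, every exit is a death, and patients receive 1 to 6 cycles (assumed). Week 12:

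| ADR hazard per day | As written | Censored at death | Death as competing event |
|---|---|---|---|
| 0.012 | 62.3% | 63.6% | 59.9% |
| 0.006 | 38.3% | 39.3% | 36.7% |

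The plan is 1.0 to 1.3 points below one standard estimate and 1.6 to 2.4 points above the other.

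**Excess time.** With 176 patients and 10 to 30% leaving early (assumed), the ceiling is 18 × 28 = 504 to 53 × 28 = 1,484 patient-days. If exits are spread evenly, it is about half that.

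**The case against.** The strongest reply is that this hardly matters. The excess is capped at 28 days per patient. At 63% with 176 patients, a simple binomial 95% half-width is 1.96 × √(0.63 × 0.37 / 176) ≈ 7 points, far wider than the shift. SAP 4 treats testing as exploratory and sets no decision rules. The crude ADR incidences and the counts by onset category do not use the censoring rule. All of this stands and limits the weight of the point. It does not make the rule correct, since sampling error does not excuse a known error in the risk set.

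A reader might infer that every rate from Week 1 to Week 24 is understated. The documents do not support that. The effect at Weeks 1 to 4 is negligible under most assumptions, and against a competing-risk estimate the rule is too high for deaths. A reader might also infer that the confidence intervals are wrong by a material amount, but no interval calculation shows this.

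Nor does the separate VOD/SOS rule prove an oversight. VOD/SOS has a much longer collection window, so early exit matters more there, and the revision history shows that its cut-off was revised specifically. That rule does show that the SAP can censor at actual discontinuation. It names no competing event for death either, so the proposed handling of death goes further than that comparator.

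Finally, transfer does not always end observation. Protocol 8.7 asks the receiving hospital for data, and SAP 5.1 and 8.2.1 provide for linked records. Censoring such patients when they leave the first hospital would discard real follow-up.

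**Conclusion.** The rule is wrong as written for patients whose observation ends before day 28 after the last dose, and right for everyone observed to that day. For live losses the ADR rates are understated by roughly 0.4 to 1.6 points at Week 12 if 15 to 25% leave early, and somewhat more if treatment is short. This assumes that exit is unrelated to ADR risk. For deaths the estimate lies between two recognised quantities and equals neither in general. The dead are censored, but up to 28 days late.

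The net direction cannot be settled from the documents, because they give no exit rate, no ADR rate for this analysis, and no split between deaths and live losses. The point concerns the accuracy of a descriptive safety estimate. It bears on no test, sample size or decision rule.

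**What to change.** Replace the censoring sentence with one to this effect: patients without the ADR are censored at the earlier of 28 days after the final dose and the end of actual observation. The end of observation is the survey discontinuation date or, for a transferred patient with linked records, the end of observation at the receiving hospital.

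Then state how death before that date is handled. The preferred choice is a competing event, using the cumulative incidence method already in SAP 8.1.4, because it estimates the share of patients who actually experience the ADR. The alternative is to censor at death and say so. If the competing-risk route is taken, the SAP should also say whether the onset quartiles are read from the cumulative incidence curve or dropped.

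The cost is one SAP sentence and a little extra programming. Discontinuation dates and reasons (Protocol 8.8.9) and death dates (Protocol 8.8.12) are already collected. The discontinuation table in SAP 8.2.1, by timing and reason, will show how many patients the change affects.
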